APPENDIX VII. GUIDANCE FOR THE SAFETY MONITERING AND MANAGEMENT OF ADVERSE EVENTS

1. Introduction

AZD4205 is a potent, oral, ATP-competitive inhibitor of JAK1 kinase. It is intended for the treatment of advanced cancer patients as monotherapy in this study.

Whilst there is no clinical experience with AZD4205, preclinical studies suggest a potential association between the use of AZD4205 and adverse events of cardiac, liver, lung etc. been observed. When the appropriate treatment of these events is instituted, they can be tolerable, allowing patients to continue receiving treatment.

The purpose of these treatment guidelines is:

- To prevent tolerable adverse events becoming intolerable for the patient and leading to discontinuation of treatment.
- To promote consistency of monitoring and treatment for specific adverse events across the AZD4205 clinical development program.

2. Cardiovascular Effects

Whilst there is no clinical experience with AZD4205, preclinical studies suggest a potential association between the use of AZD4205 and the occurrence of cardiovascular events has been observed. As a result, sponsor has chosen to include Digital ECG, Echo/MUGA (multigated acquisition scan) and highly-sensitive Troponin T and NT-pro BNP levels in the clinical safety monitoring.

It is important that patients are fully informed that potential cardiac events may occur during treatment with AZD4205.

Safety monitoring with ECGs:

- Twelve-lead triplicate ECG will be performed at the visit indicated in the Study Plan.
- A standardized ECG machine should be used, and the patient should be examined using the same machine throughout the study.
- The digital ECGs should be analyzed by an ECG Central lab.
- Single ECGs should also be performed at the time of significant LVEF drop and on occurrence of any cardio-respiratory adverse event of non-obvious cause (obvious causes will be managed in accordance with local clinical practice). For patients with new or worsening respiratory symptoms (such as dyspnea, cough), an ECG is recommended and additionally at the discretion of the investigator if clinically indicated.
- During the study, clinically significant abnormal ECG findings not present at baseline should be reported as an AE. It is recommended that asymptomatic ECG findings should be adjudicated by an expert reader if case they are reported as AEs. If present, the clinical signs

- and symptoms associated with the abnormal finding should be reported as the AE with the ECG abnormality given as explanatory information.
- Management of QTc prolongation: A QTcF > 500 ms is an independent criterion for individual pro-arrhythmic risk. Any QTcF > 500 ms should trigger a repeat ECG timepoint in 5-10 min to confirm the finding. If confirmed, patient will be withdrawn from study Patients experiencing QTc interval prolongation with signs/symptoms of serious arrhythmia will not be permitted to restart study treatment.

Safety monitoring with Echocardiogram/MuGA:

- The modality of the cardiac function assessments must be consistent within a patient i.e. if echocardiogram is used for the screening assessment then echocardiogram should also be used for subsequent scans.
- The patients should also be examined using the same machine and operator whenever
 possible, and quantitative measurements should be taken. Recommendations include having
 complete high quality standardized 2-D with Doppler echocardiographic examinations
 performed by an experienced sonographer and include evaluation of both systolic and
 diastolic left ventricular function.
- Ejection fraction determinations should be determined quantitatively based on bi-plane measurements of end diastolic and end systolic left ventricular volumes.
- Any symptomatic decrease in LVEF will prompt the discontinuation of the treatment and a cardiac consultation.
- Below table is the reference for the management of asymptomatic decrease of LVEF:

Absolute EF	Decrease from Baseline <10%	Decrease from Baseline 10-15%	Decrease from Baseline >15%
55% or above	Continue	Continue	Interruption*. ECHO/MUGA in 3 weeks. If value back to baseline, consider dose resumption.
54-40%	Continue	Interruption. Cardiac consultation. ECHO/MuGA in 3 weeks. If LVEF above 55% consider dose resumption	Discontinue. Cardiac consultation
Below 40%	Interruption. Cardiac consultation	Discontinue. Cardiac consultation	Discontinue. Cardiac consultation

Footnote: *A subject with EF decreasing by > 15% and remaining > 55% would have to start from > 70%, i.e. a very high normal. Hypovolemia, hyperthyroidism and hypertrophic/constrictive/significant restrictive cardiomyopathy should be considered and ruled out.

Troponin and NT-pro BNP

- Both high sensitivity troponin T testing (TnT or hs-TnT) and NT-pro BNP will be performed.
- A core/central laboratory is recommended to ensure that the same assay is used for a given study and, if feasible, for all studies in the same program to minimize systematic errors. When using a central laboratory, if a local laboratory is used for ad hoc cTn testing for the purpose of patient management, a duplicate sample should be sent to the core/central laboratory whenever possible.
- When clinically indicated by unexpected significant TnT rise, a TnT sample should be repeated and evaluation by ECHO considered. When indicated by symptoms and signs of suspected ischemic event, an increased TnT should trigger TnT sampling schedule. If there is an unexpected rise in cTnT, additional time points are needed to capture the time course of the cTnT changes, repeating the test at appropriate intervals. A core laboratory should be utilized to ensure the same assay is used in the study.
- It was not suggested to give a specific exclusion or discontinuation cut-off values for TnT in patients without symptoms or signs of unstable ischemic cardiac disease or progressing symptomatic congestive heart failure.

Referral to cardiologist

- Patients experiencing QTc interval prolongation with signs/symptoms of serious arrhythmia should be referred to cardiologist.
- Cardiologist examination findings should be documented in the patient's notes and reported to sponsor if required.
- In addition, a report should be provided to sponsor detailing:
 - o Cardiologist examination performed.
 - o Findings or change from baseline
- Treatment administered should be captured on the CRF

3. Pulmonary monitoring

- AZD4205 is a potent, oral, ATP-competitive inhibitor of JAK1 kinase. It is intended for the treatment of advanced cancer patients as monotherapy in this study.
- Preclinical studies suggest a potential association between the use of AZD4205 and the occurrence of lung events. Thus, patients with previous medical history of ILD (interstitial lung disease), drug induced ILD, radiation induced pneumonitis need steroid treatment, or any evidence of clinically active ILD, should be excluded from AZD4205 related clinical studies.
- On the other hand, serious infection including opportunistic infection such as pneumocystis carinii pneumonia (PCP) is an identified risk for many approved JAK inhibitors (e.g. tofacitinib and ruxolitinib). Given the fact that patients with lymphoproliferative disorders (e.g. lymphoma) are at a high risk for PCP infection, prophylaxis for PCP should be taken into consideration during the study treatment. Trimethoprim/sulfamethoxazole (TMP/SMZ) is

[figure not shown]
the preferred drug for the primary prophylaxis of PCP infections in adults. The recommended dose is a single-strength (80/400 mg) tablet daily.

- It is important that patients are fully informed that potential pulmonary events may occur during treatment with AZD4205.
- If there is any suspicion of interstitial lung disease (e.g. abnormal findings on CT scans, DLCO decrease ≥ 15%, or any related pulmonary symptoms/signs), dosing with AZD4205 should be interrupted whilst further investigations (a full diagnostic workup) are performed.
- Sometimes, the atypical pneumonia due to infection is difficult to differentiate from pneumonitis only based on radiological findings, e.g. abnormal ground glass opacity (GGO) on CT scans. Thus, a full diagnostic workup (e.g., HRCT, pathogen detection tests, hematology tests) is highly recommended, when a pulmonary event is suspected. The full diagnostic workup is aimed at excluding conditions such as lymphangitis carcinomatosis, infection, allergy or pulmonary hemorrhage, and the details are as below (see Figure 3):
 - ➤ High resolution CT (HRCT) scan is recommended when a pulmonary event is suspected, e.g. abnormal findings on CT scans, DLCO decrease ≥ 15%, or any related pulmonary symptoms/signs.
 - > The diagnostic workup should cover routine diagnostic tests for pulmonary events (e.g. routine hematology test, blood biochemistry), and other diagnostic tests for differential diagnosis to exclude conditions such as infection, lymphangitis carcinomatosis, allergy or pulmonary hemorrhage. For example, procalcitonin, β-D-Glucan, blood/sputum culture, pneumocystis PCR, Cytomegalovirus (CMV) PCR, mycoplasma PCR, tuberculosis diagnostic test, respiratory virus detection (including COVID-19).
 - In the presence of confirmatory HRCT scans, where other causes of respiratory symptoms have excluded though the full diagnostic workup, a diagnosis of drug induced pneumonitis should be considered, and study treatment should be permanently discontinued. In the absence of a diagnosis of pneumonitis, study treatment may be started.
- Please complete the eCRF and inform sponsor as soon as a potential pulmonary event is identified. The study team will send a pneumonitis questionnaire, in order to collect more information about the event for full review and reporting.

Figure 3 ILD/Pneumonitis Assessments Flow Chart

[figure not shown]
If any of the following occur or worsen while on study and can not be categorically be clinically ascribed to a cause other than AZD4205:

- New or worsening pulmonary symptoms (e.g. dyspnea, cough)
- · Radiological abnormality suggestive of interstitial lung disease
- Decrease in lung function test (DLCO decrease $\geq 15\%$)

A full diagnostic workup should be performed, including:

- High resolution CT (HRCT) scan
- · Routine diagnostic tests for pulmonary events (e.g. routine hematology test, blood biochemistry)
- Other diagnostic tests for differential diagnosis to exclude conditions such as lymphangitis carcinomatosis, infection, allergy or pulmonary hemorrhage. For example, procalcitonin, β-D-Glucan, blood/sputum culture, pneumocystis PCR, CMV PCR, mycoplasma PCR, tuberculosis diagnostic test, respiratory virus detection (including COVID-19)

following agreement with sponsor study physician

4. Infection

permanently discontinued

Serious infections are identified risk of many approved JAK inhibitors (e.g. ruxolitinib, tofacitinib and baricitinib). On the other hand, previous heavily treated PTCL patient are also at a high risk for infections, especially opportunistic infections. So far, infections including pneumocystis pneumonia, herpes zoster and cytomegaloviral reactivations were reported in clinical studies with AZD4205.

Patients with active infection should be excluded from participating in this study, e.g. infections requiring oral or intravenous antimicrobial therapy. Subjects will be monitored for development of any infection (viral, bacterial, and fungal).

Prophylaxis for pneumocystis pneumonia

Pneumocystis carinii infection causes life-threatening pneumonia (PCP; also known as PJP) in patients with immunosuppression due to underlying malignancy, organ transplantation or other

conditions. It's known that heavily treated patients with hematological malignancies are at a high risk of PCP infection, and many approved JAK inhibitors also observed PCP infection. Hence, adequate prophylaxis is critical in high-risk conditions (Cordonnier C et al. 2016). Most cases of PCP occur from reactivation of latent infection, although cases of person-to-person transmission have been reported. In a Cochrane meta-analysis (including 1155 adult patients with acute leukemia and recipients of an HSCT and solid organ transplant), the incidence of PCP was reduced by 91% [relative risk (RR) 0.09] with prophylaxis compared with placebo, no treatment or treatment with antimicrobial agents showing no activity against P. jirovecii (e.g. quinolones) (Green H et al. 2007). Pneumocystis pneumonia has been reported in the clinical study with AZD4205. Therefore, for all patients during the treatment, pneumocystis prophylaxis is required. Please follow institutional guidelines or refer to below guidance (Maertens J et al. 2016, L. Cooley et al. 2014).

Trimethoprim/sulfamethoxazole (TMP/SMZ) is the preferred drug for the primary prophylaxis of Pneumocystis infections in adults. The recommended dose is either a single-strength (80/400 mg) tablet daily or a double-strength tablet (160/800 mg) three times weekly. Limitations in TMP/SMX prophylaxis include documented hypersensitivity, renal impairment, myelosuppression and gastrointestinal disturbance. The true rate of adverse reactions is unknown, but in the adult HSCT population it is estimated to be in the range of 5–15%, and in children it is much lower (Souza JP et al.1999).

Second-line agents for PJP chemoprophylaxis may be given to the patients if TMP/SMZ is intolerant or contraindicated, including dapsone, atovaquone or pentamidine (see Table 17).

Table 17 Dosing schedule for PCP chemoprophylaxis for adult patients with hematological malignancies

	Dosing schedule		
	80 + 400 mg (one SS tablet) orally, daily		
TMP-SMZ	Or		
	160 + 800 mg (one DS tablet) orally, three times a week		
Dapsone	100 mg orally, daily		
Pentamidine	300 mg inhaled through nebuliser, every 4 weeks (administered through a jet- nebuliser producing a droplet size of 1–2 microns)		
Atovaquone	1500 mg orally, daily with a high-fat meal		

Monitoring and management of cytomegaloviral infections

A few cases of cytomegaloviral (CMV) infection, including CMV chorioretinitis and/or retinal disorders related to CMV infection, were reported in the clinical trials of AZD4205. For patients with history of CMV infection that required treatment, prophylactic treatment and monitoring for reactivation via serology or viral load detection per institutional guidelines is recommended.

Besides, based on the nature and severity of CMV chorioretinitis, patients should be educated to report any changes in vision or ocular symptoms directly to their ophthalmologist.

Specially, ophthalmic examinations should be performed for all patients at baseline, Cycle 3 and then every 3 cycles (approximately every 2 months) after enrolment. The recommended ophthalmic examinations include visual acuity (corrected), intraocular pressure, slit lamp examination, and dilated ophthalmoscopy. If intraocular infection of CMV is suspected, a biopsy of intraocular fluid (aqueous humor and/or vitreous humor, depending on the involvement of the disease) is recommended to confirm the pathogen.

The following ocular adverse events should be graded according to Table 18, and if the causality is considered to be related with the study intervention, the dose should be also modified accordingly.

Table 18 Addendum to Grading of Ocular Adverse Event and Dose Modifications of Ocular Adverse Reactions

Adverse Event/Reaction	Description	Grade	Actions in Dose Modification
Keratitis	Clear cornea, no epithelial defects	Grade 0	Dosing not interrupted
	Nonconfluent superficial keratitis; asymptomatic; clinical or diagnostic observation only; intervention not indicated	Grade 1	Dosing not interrupted
	Confluent superficial keratitis; symptomatic; a cornea epithelial defect, or 3-line or less decreased vision in best corrected distance visual acuity (BCVA) from baseline	Grade 2	Drug interruption until resolved to nonconfluent superficial keratitis, then resume dose
	Corneal ulcer or stromal opacity; marked BCVA decrease, worse than 20/40 or more than 3 lines of decreased vision from baseline, up to 20/200; limiting self care activities of daily living	Grade 3	Drug interruption until resolved, then reduce dose to 75 mg
	Corneal perforation; or BCVA of 20/200 or worse in the affected eye	Grade 4	Discontinue participant from study treatment
	No vasodilation, no epithelial defects	Grade 0	Dosing not interrupted
	Nonconfluent superficial punctate defects, mild vasodilation	Grade 1	Dosing not interrupted
Conjunctivitis	Confluent superficial punctate staining, moderate to severe vasodilation.	Grade 2	Drug interruption until resolved to nonconfluent superficial keratitis, then resume dose
	Conjunctival ulcer or neovascularization.	Grade 3	Drug interruption until resolved, then reduce dose to 75 mg
	BCVA of 20/200 or worse in the affected eye	Grade 4	Discontinue participant from study treatment
Iritis/Uveitis	Clear anterior chamber	Grade 0	Dosing not interrupted

Adverse Event/Reaction	ion Description		Actions in Dose Modification
	Trace cell in anterior chamber	Grade 1	Dosing not interrupted
	1-2+ cell or flare in anterior chamber	Grade 2	Drug interruption until resolved to Grade 0 or 1 and then resume dose
	3+ cell or flare in anterior chamber; intermediate posterior or pan-uveitis	Grade 3	Drug interruption until resolved to Grade 0 or 1, then reduce dose to 75 mg
	Hypopyon; or BCVA of 20/200 or worse in the affected eye	Grade 4	Discontinue participant from study treatment
	No detachment	Grade 0	Dosing not interrupted
Serous detachment of retinal pigment epithelium	Detachment which starts to resolve at or within 2 weeks	Grade 1	Dosing not interrupted
	Detachment which does not start to resolve at or within 2 weeks	Grade 2	Delay dose until detachment starts to resolve, then maintain dose.
	Detachment which does not start to resolve within 2 months	Grade 3	Drug interruption until detachment starts to resolve, then reduce dose to 75 mg
	BCVA same as baseline BCVA	Grade 0	Dosing not interrupted
	Intervention not indicated	Grade 1	Dosing not interrupted
Blurred vision	BCVA worse than baseline but no worse than 20/40 and better; or 3 lines or less decreased vision from known baseline; limiting instrumental activities of daily living	Grade 2	Dosing not interrupted
	BCVA worse than baseline but no worse than 20/200; or more than 3 lines of decreased vision from known baseline; limiting self care activities of daily living	Grade 3	Drug interruption until resolved as baseline or 20/40 whichever is worse, then resume dose
	BCVA 20/200 or worse	Grade 4	Drug interruption until resolved as baseline or 20/40 whichever is worse, then reduce to 75 mg
	No evidence of retinal involvement	Grade 0	Dosing not interrupted
	No evidence of retinal involvement	Grade 1	Dosing not interrupted
Cytomegaloviral chorioretinitis	No evidence of retinal involvement	Grade 2	Dosing not interrupted

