5.1.3 Dose modifications

5.1.3.1 Toxicity management and dose modifications to AZD4205

If a patient has a treatment emergent adverse event (TEAE) at least possibly related to AZD4205, then dose interruptions/holds with possible modifications as described in Table 1 should be implemented. Deviations from these guidelines may occur based on the clinical judgment of the investigator with notification to the Sponsor. For managing toxicity related to the eye, refer Appendix VII.

Table 1 Dose Interruptions/Modifications for Toxicities Observed in the Study

Category	Toxicities needing immediate interruption	Dose modification plan
	$\mathrm{ANC} < 0.5 \times 10^9/\mathrm{L}$	Immediate interruption of AZD4205. Once toxicity has resolved to recovery to ≤ Grade 2 or baseline within 14 days of onset: Resume at the same dose for the 1st occurrence of the event Resume at the reduced dose for the 2nd occurrence of the event Permanent discontinue for the 3rd occurrence of the event
Hematological	Platelet count $< 25 \times 10^9/L$	Immediate interruption of AZD4205 Once toxicity has resolved to recovery to ≤ Grade 2 or baseline within 21 days of onset: Resume at the same dose for the 1st occurrence of the event Resume at the reduced dose for the 2nd occurrence of the event Permanent discontinue for the 3rd occurrence of the event
toxicity	Grade 3 febrile neutropenia	Immediate interruption of AZD4205 Once toxicity has resolved to recovery to ≤ Grade 2 or baseline within 14 days of onset: Resume at the reduced dose for the 1st occurrence of the event, unless the toxicity can be safely and reliably controlled to ≤ Grade 2 or baseline with appropriate treatment, (dose may restart at 150 mg once daily after reaching an agreement with the sponsor). If the same non-hematological toxicity requiring dose interruption occurs again, AZD4205 should be permanently discontinued.
	Grade 3 thrombocytopenia with significant bleeding Other Grade 4 or unmanageable hematological toxicity(ies)	Permanent discontinuation Immediate interruption of AZD4205

		Once toxicity has resolved to recovery to \leq Grade 2 or baseline within 14 days of onset:
		Resume at the same dose for the 1st occurrence of the event
		 Resume at the reduced dose for the 2nd occurrence of the event
		 Permanent discontinue for the 3rd occurrence of the event
	QTcF > 500 ms absolute or > 60 ms increase from baseline	Permanent discontinuation

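### Table 18 restarts dosing after Grade 2 conjunctivitis on a keratitis finding; the restart should be at conjunctivitis Grade 0 or 1

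*Protocol*

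**What the plan says.** Section 5.1.3.1 takes eye toxicity out of the general dose-modification scheme: "For managing toxicity related to the eye, refer Appendix VII". Appendix VII then says that the listed ocular events are graded by Table 18 and, when judged related to study treatment, that the dose is modified by the same table.

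For conjunctivitis, Table 18 defines Grade 1 as "Nonconfluent superficial punctate defects, mild vasodilation" and Grade 2 as "Confluent superficial punctate staining, moderate to severe vasodilation". Grades 0 and 1 do not interrupt dosing. The Grade 2 action is "Drug interruption until resolved to nonconfluent superficial keratitis, then resume dose".

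The keratitis Grade 2 action is the same sentence. Keratitis Grade 1 is defined as "Nonconfluent superficial keratitis; asymptomatic; clinical or diagnostic observation only; intervention not indicated".

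**The concern.** The restart condition for a conjunctival event is a corneal finding. It belongs to the row above, where it makes sense, and it does not correspond to any grade on the conjunctivitis scale. It also says nothing about vasodilation, although moderate to severe vasodilation is half of what makes the event Grade 2.

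A restart rule tells the site when a held patient may be re-exposed. If the rule names the wrong finding, sites have to supply their own threshold and may choose different ones. What is at stake is the safety of restarting in the patients affected. To a lesser degree, so is the consistency of the interruption and relative dose intensity summaries planned in SAP section 5.4.6.

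**Working it through.** No formula applies. The check compares rows within Table 18.

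**Step 1: the conjunctivitis scale against the restart condition.**

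| Grade | Surface component | Vasodilation | Dosing |
|---|---|---|---|
| 0 | no epithelial defects | none | continues |
| 1 | nonconfluent punctate defects | mild | continues |
| 2 | confluent punctate staining | moderate to severe | held |
| 3 | conjunctival ulcer or neovascularization | not stated | held, then 75 mg |
| 4 | defined by visual acuity only | not stated | stopped |

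Descriptions that mention keratitis: 0 of 5. Vasodilation is a component of Grades 0, 1 and 2, and the restart condition does not refer to it.

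**Step 2: applying the rule literally.** Take a patient with Grade 2 conjunctivitis and a clear cornea. Either the condition is already satisfied, because the cornea is at or better than nonconfluent superficial keratitis, or it cannot be applied, because there is no keratitis to resolve. In neither case does the cell give a conjunctival threshold. Vasodilation could remain moderate to severe, and the restart condition would not prevent dosing.

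**Step 3: how the other Grade 2 rows restart.** Table 18 has 6 events, each with a Grade 2 row. Blurred vision and CMV chorioretinitis do not interrupt dosing at Grade 2, which leaves 6 − 2 = 4 rows that hold it.

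| Event | Grade 2 restart condition | Own finding? |
|---|---|---|
| Keratitis | its Grade 1 finding | yes |
| Conjunctivitis | keratitis Grade 1 finding | no |
| Iritis/uveitis | "Drug interruption until resolved to Grade 0 or 1 and then resume dose" | yes |
| Serous detachment | when detachment starts to resolve | yes |

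So 3 of 4 restart on their own event and 1 of 4 does not. The conjunctivitis rows also show where the restart should fall: Grades 0 and 1 are the two grades at which dosing continues.

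**Step 4: the 75 mg rows (secondary).** Grade 3 keratitis, conjunctivitis, uveitis, serous detachment and CMV chorioretinitis all end in 75 mg, which is 5 rows. Grade 3 blurred vision resumes the dose, but its Grade 4 action is "Drug interruption until resolved as baseline or 20/40 whichever is worse, then reduce to 75 mg". That makes 5 + 1 = 6 rows, and none covers a patient already at 75 mg. Section 5.1.3.1 does have a rule to discontinue such a patient, and another to discontinue when an interruption exceeds its maximum, but it ties both to Table 1. The Table 1 limits are 14 or 21 days from onset, with 14 days for other Grade 3 non-hematological toxicity. Serous detachment Grade 3 is defined as "Detachment which does not start to resolve within 2 months", so either limit would have expired before the grade could be assigned. The interruption limit therefore cannot simply be carried over to every row.

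**The case against.** The strongest reply is that the intent is easy to infer. Table 18 assigns actions by grade, so a patient still at Grade 2 remains in a row that says hold, and a patient at Grade 0 or 1 is in a row that says continue. The two scales also share vocabulary: both move from nonconfluent to confluent superficial change between Grades 1 and 2, so the misplaced phrase tracks part of conjunctivitis Grade 1. Eye examinations are done by a specialist. Section 5.1.3.1 allows deviations on clinical judgment, with notice to or agreement from the sponsor.

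The effect on summaries is also unmeasured. The protocol reports CMV-related eye events but no conjunctivitis. The SAP was written against protocol version 5.0, and its visit schedule has no eye-examination row, so the documents do not show how much Part B dosing Table 18 governed.

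These points limit the consequence. They do not make the cell right. Inferring the restart point from neighbouring rows means setting aside what the cell says. The shared vocabulary still leaves out vasodilation. Permission to deviate does not correct a wrong default. That the sentence was carried over from the keratitis row is an inference, although the verbatim match supports it strongly; the defect stands however it arose.

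On the 75 mg point, no lower dose is defined anywhere, so discontinuation is the likely intent. That part is a clarification only.

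**Conclusion.** The concern holds. One of the four Grade 2 rows that hold dosing restarts on another event's finding, and no other text in the protocol gives a conjunctivitis restart rule. This is an error in an operative dosing rule and should be corrected.

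Its reach is limited to related Grade 2 conjunctivitis, whose frequency the documents do not give, and to descriptive summaries of interruption and dose intensity. The primary ORR analysis, the sample size and the error rates are unaffected. That sites would in fact restart at different points is a reasonable expectation from the wording, not something the documents show.

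The conclusion that Grade 0 or 1 was meant rests on the table's own structure: those grades do not interrupt dosing, and the uveitis row uses that form. The 75 mg gap is secondary and would not warrant a change by itself.

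**What to change.** Reword the conjunctivitis Grade 2 action so that dosing is held until conjunctivitis is Grade 0 or 1 (nonconfluent punctate defects with no more than mild vasodilation, or better) and then resumes. This follows the form of the uveitis Grade 2 row.

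At the same time, add one footnote to Table 18 stating (a) that a patient already at 75 mg who meets a row requiring reduction discontinues, as in section 5.1.3.1, and (b) whether the Table 1 maximum interruption applies to ocular events. If it does, serous detachment Grade 3 needs an exception.

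The cost is a few words in one cell and one footnote. No new data, visits or procedures are needed.

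### Table 18 places blurred vision at a BCVA of exactly 20/200, and in many cases worse, in both Grade 3 (resume dose) and Grade 4 (reduce to 75 mg)

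*Protocol*

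**What the plan says.** Protocol Section 5.1.3.1 sends management of eye toxicity to Appendix VII, and Section 6.5.3 sends the grading of specific ocular events there. Appendix VII states: "The following ocular adverse events should be graded according to Table 18". It adds that the dose is to be modified accordingly when the event is judged related to study drug. For such an event, the grade decides the dose.

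The blurred vision row of Table 18 reads:

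| Grade | Acuity clause | Daily-living clause | Action |
|---|---|---|---|
| 2 | "BCVA worse than baseline but no worse than 20/40 and better; or 3 lines or less decreased vision from known baseline" | instrumental activities limited | dosing not interrupted |
| 3 | "BCVA worse than baseline but no worse than 20/200; or more than 3 lines of decreased vision from known baseline" | self care limited | "Drug interruption until resolved as baseline or 20/40 whichever is worse, then resume dose" |
| 4 | "BCVA 20/200 or worse" | none | "Drug interruption until resolved as baseline or 20/40 whichever is worse, then reduce to 75 mg" |

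Grade 0 is acuity unchanged from baseline. Grade 1 has no acuity limit.

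In the same table, keratitis Grade 3 follows its line count with an upper limit: "worse than 20/40 or more than 3 lines of decreased vision from baseline, up to 20/200". Keratitis Grade 4 is "Corneal perforation; or BCVA of 20/200 or worse in the affected eye".

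**The concern.** A grading scale that drives dosing should give one action for each state of the patient. Here two adjacent grades share their boundary value, and one of them has an alternative with no upper limit. The interruption rule is the same in both grades; the dose after recovery is not. One grade returns the patient to the same dose and the other reduces it to 75 mg.

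At stake is consistent dosing after severe loss of vision. The value 20/200 is the table's own cut-point, and it also appears in the Grade 4 cells for keratitis, conjunctivitis and iritis/uveitis. Eye events are an expected part of this programme: Appendix VII reports CMV chorioretinitis and related retinal disorders in trials of the drug, and the Part B schedule includes regular eye examinations.

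**Working it through.** **Step 1: the boundary (no chart assumption).** Put BCVA = 20/200 into each acuity clause, with a better baseline.
- Grade 3, no worse than 20/200: true.
- Grade 4, 20/200 or worse: true.

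The daily-living clause does not remove the overlap. If it is a joint requirement for Grade 3, a patient at 20/200 with limited self care still meets Grade 3, and also meets Grade 4, which has no such clause. If it is not required, every patient at 20/200 with a better baseline meets both.

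**Step 2: beyond 20/200 (chart assumption needed).** The documents name no chart. Assume 0.1 logMAR per line, giving the ladder 20/20, 25, 32, 40, 50, 63, 80, 100, 125, 160, 200, 250, 320, 400. Lines lost = current position minus baseline position. Acuity clauses as printed:
- Grade 2: (worse than baseline and 20/40 or better) or (1 to 3 lines lost)
- Grade 3: (worse than baseline and no worse than 20/200) or (more than 3 lines lost)
- Grade 4: 20/200 or worse

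| Baseline | Lines lost at 20/200, 250, 320, 400 | Grades met |
|---|---|---|
| 20/20 | 10, 11, 12, 13 | 3 and 4 at all four |
| 20/40 | 7, 8, 9, 10 | 3 and 4 at all four |
| 20/100 | 3, 4, 5, 6 | 2, 3 and 4 at 20/200; 3 and 4 at the other three |

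All 12 baseline-level pairs at or beyond 20/200 meet both Grade 3 and Grade 4 on acuity. The fall from 20/100 to 20/200 also meets Grade 2's line-count alternative, under which dosing is not interrupted.

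**Range for the assumption.** With lines twice as coarse (0.2 logMAR), halve the line counts for the nine pairs beyond 20/200:
- From 20/20: 5.5, 6, 6.5. All exceed 3, so Grades 3 and 4.
- From 20/40: 4, 4.5, 5. All exceed 3, so Grades 3 and 4.
- From 20/100: 2, 2.5, 3. None exceeds 3, so Grades 2 and 4.

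The overlap of Grades 3 and 4 beyond 20/200 is then 6 of 9 pairs instead of 9 of 9. All nine still meet two grades. The overlap at exactly 20/200 does not change.

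**Step 3: unchanged poor baseline.** An eye that starts at 20/200 and stays there is Grade 0 (unchanged), yet it also meets Grade 4 as printed, because that cell does not require worsening. The exclusion criteria in Protocol Section 4.2 contain no visual acuity limit.

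**Step 4: the proposed wording.** With Grade 3 and Grade 2's line-count alternative limited to acuity better than 20/200, the 12 pairs in the table meet Grade 4 only, so 0 of 12 overlap. With Grade 4 requiring worsening, the unchanged 20/200 eye is no longer Grade 4. Pairs better than 20/200 are graded exactly as now.

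**The case against.** **The intent is clear and the higher grade applies.** Three other rows place 20/200 or worse at Grade 4, and a severe state often also meets lower-grade wording. This is fair as evidence of intent, and it supports giving 20/200 to Grade 4. But Table 18 does not state the convention. SAP Section 5.7.1 counts a participant with several events under the most severe; it does not grade a single event. Table 18 calls itself an addendum, and CTCAE v5.0 may hold a convention, but the documents do not reproduce one.

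**Judgement and diagnosis reduce the exposure.** Section 5.1.3.1 permits deviations, in one place with notification to the sponsor and in another with agreement of the Medical Monitor/Sponsor. Section 6.5.3 prefers a diagnosis to a symptom, so an event with an identified cause such as keratitis or uveitis would usually use its own row. Both points stand and limit the size. Neither says which blurred vision grade applies.

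**Table 1 could settle it.** Its Grade 4 non-haematological action is permanent discontinuation, but Section 5.1.3.1 routes eye toxicity to Appendix VII.

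A reader might infer more than the documents support:
- *Grades 2 and 3 also contradict each other.* On acuity alone they overlap, for example at 20/25, 20/32 and 20/40 from a 20/20 baseline. If the daily-living clauses are required, they separate the two grades. The table does not say how the clauses combine, so this is not counted.
- *Keratitis has the same contradiction.* Its Grade 3 upper limit can be read as stopping short of 20/200, so this is arguable only.
- *The adverse event tables or the efficacy results are affected.* SAP Section 4.3.2 grades adverse events by CTCAE v5.0 and its visible text does not mention Table 18. ORR and power do not use these grades.

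**Conclusion.** Wrong as written, minor. At exactly 20/200 the printed row gives two dose actions, with no chart assumption and whichever way the daily-living clause is read. The extension beyond 20/200 follows from the uncapped line count; how far it reaches depends on the chart (9 of 9 illustrative pairs at 0.1 logMAR per line, 6 of 9 at 0.2). These pairs are hypothetical chart levels, not patients, and the documents give no frequency for such events. The consequence is limited to inconsistent dosing of individual patients with a related event at or beyond 20/200.

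**What to change.** Change three blurred vision cells in Table 18 at the next protocol amendment:
- **Grade 3:** replace the limit *no worse than 20/200* with *better than 20/200*, and add *with BCVA better than 20/200* to the line-count alternative.
- **Grade 2:** add *with BCVA better than 20/200* to the line-count alternative only.
- **Grade 4:** *BCVA worse than baseline and 20/200 or worse*, so that an unchanged poor baseline stays Grade 0.

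Leave the daily-living clauses, the rest of Grade 2 and the keratitis row as they are.

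Two wider remedies are tempting and should be avoided:
- **A general note that the higher grade applies.** On the printed acuity clauses, from a 20/20 baseline, it would make 9 of the 10 levels from 20/25 to 20/200 Grade 3 and none Grade 2. With the present Grade 4 cell it would also send an unchanged 20/200 eye to 75 mg.
- **Requiring Grade 2 to be both 20/40 or better and 3 lines or less.** This removes the allowance for poor baselines. Take baselines 20/16 to 20/160 at 0.1 logMAR per line. There are 27 pairs with a loss of 3 lines or less and acuity better than 20/200: 8 baselines × 3, plus 2, plus 1. Only 9 of them (3 + 3 + 2 + 1) are 20/40 or better. The other 18, including 6 one-line losses, would move from no interruption to interruption.

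Cost: three reworded cells and no new data collection. Protocol Section 10 requires IRB/IEC and regulatory approval of amendments, so this should travel with other changes. The downside is that patients who worsen to exactly 20/200 from a related event are always reduced to 75 mg; the medical monitor should confirm that this is intended. The change does not settle how the Grade 2 and Grade 3 clauses combine at better acuities.
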